- 14. Presence of orthostatic hypotension at screening: a decrease in systolic blood pressure (at least 20 mm Hg) or diastolic blood pressure (at least 10 mm Hg) within 3 minutes of the subject standing up, compared to pressures obtained while sitting;

- 15. Any of the following laboratory test results at screening:
  - Hemoglobin < 10 g/dL
  - WBC  $< 3.0 \times 10^9/L$
  - Neutrophils  $< 1.5 \times 10^9/L$
  - Lymphocytes  $< 0.5 \times 10^9/L$
  - Platelets  $< 100 \times 10^9 / L$
  - Aspartate aminotransferase (AST) and/or alanine aminotransferase (ALT) > 2 times the upper limit of normal;
- 16. Estimated GFR < 50 mL/min/1.73m^2 (calculated using Modification of Diet in Renal Disease (MDRD));
- 17. Inability to swallow oral capsules, or a history of gastrointestinal malabsorption that would preclude the use of oral medication;
- 18. If female, is pregnant or lactating;
- 19. If a sexually active female, is not surgically sterile or at least 2 years postmenopausal, or does not agree to utilize a highly effective hormonal method of contraception (an IUD, or vasectomized male partner is also acceptable), in combination with a barrier method, from screening through at least 4 weeks after the completion of study treatment;
- 20. Documented inability to tolerate amantadine, or history of suicidal ideation or suicide attempt during prior amantadine use;
- 21. History of hypersensitivity or allergic reaction to amantadine, rimantidine, or memantine, or to any of the excipients used in the study medication capsules (see Section 8.7):
- 22. Received live attenuated influenza vaccine within 2 weeks prior to enrollment (amantadine may interfere with the efficacy of live attenuated vaccine);
- 23. Current treatment with carbonic anhydrase inhibitors, sodium bicarbonate, or urinary acidification agents, quinine, quinidine, triamterene, or trimethoprim (see Appendix E);
- 24. Current treatment with medications that act primarily by blocking dopamine receptors and current treatment with medications that prolong the QT interval and have a known risk of torsades de pointes (see Appendix E). Subjects who are able to appropriately discontinue these agents at least 60 days prior to screening will be eligible for screening;
- 25. Treatment with an investigational drug (other than ADS-5102) or device within 30 days prior to screening;
- 26. Treatment with an investigational biologic within 6 months prior to screening;

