# 12.3. Recording Adverse Events

Out of range clinical laboratory findings (e.g., clinical chemistry, hematology) or findings on other assessments (e.g., electrocardiogram, X rays, vital signs) per se are not reported as AEs. However, if the out of range finding that is deemed clinically significant or is associated with signs and/or symptoms must be recorded as an AE (and additionally as an SAE if it meets the criteria of being serious; see Section 12.1.4), as described above.

The Investigator should exercise medical and scientific judgment in deciding whether an out of range clinical laboratory finding or finding on other assessment is clinically significant. Usually, the abnormality should be associated with a clinically evident sign or symptom, or be likely to result in an evident sign or symptom in the near term, in order to be considered clinically significant. A clinically significant laboratory abnormality in the absence of clinical symptoms may jeopardize the subject and may require intervention to prevent immediate consequences. For example, a markedly low serum glucose concentration may not be accompanied by coma or convulsions, yet be of a magnitude to require glucose administration to prevent such sequelae.

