8.8 Treatment Compliance

Treatment compliance data will not be integrated. Summaries are provided in the individual study results.

9 Safety Analysis

Safety endpoints will be summarized using integrated data by treatment/analysis group from the time of first dose and include all available safety data. No formal statistical testing is planned.

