9.3 Clinical Laboratory Evaluations

Clinical laboratory data for liver and renal function parameters will be integrated, listed, and summarized for the Safety population. Summaries for all other parameters are available in the individual study reports.

Laboratory assessments for these parameters were performed by a central laboratory. All summaries will be based on the SI units provided by the central lab.

Maximum on-treatment values will be summarized for the liver function parameters and minimum on-treatment values will be summarized for the renal function parameters. For both groups, the change from baseline to the maximum/minimum value will be presented.

All clinical laboratory measures will be classified as Low, Normal, or High, or Normal/Abnormal according to the normal ranges. These categorical data will be summarized in shift tables comparing the results at the baseline visit with the most abnormal results over the treatment period.

Liver function parameters include:

- Bilirubin
- Alkaline phosphatase
- γ-glutamyltransferase
- Alanine aminotransferase
- Aspartate aminotransferase

Renal function parameters include:

- Blood urea nitrogen
- Creatinine
- Estimated GFR MDRD-NKDEP
- Estimated GFR Cockcroft-Gault

Estimated GRF – Cockcroft-Gault values are not reported in the individual study databases and will be calculated as follows:

Integrated Summary of Safety for ADS-5102

Date Issued: 13Nov2015

eCreatinine Clearance $(ml/min/1.73 m^2) =$

[1.73 \times (140 – age) \times wt (kg) \times (0.85 if female) / Serum creatinine (mg/dL) \times 72 \times Body Surface Area;

Creatinine in mg/dL is rounded to 1 decimal place prior to applying the Cockcroft-Gault equation.

The equation to calculate Body surface area is described as following:

Body Surface Area(m²) = [weight (kg) \times height (cm)/3600]^{1/2}

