Normal	xx (xx.x)	xx (xx.x)	xx (xx.x)	xx (xx.x)	
High	xx (xx.x)	xx (xx.x)	xx (xx.x)	xx (xx.x)	
Missing	xx (xx.x)	xx (xx.x)	xx (xx.x)	xx (xx.x)	

Note: Baseline is defined as last available value prior to ther first dose of study medication for a particular treatment. The worst value is defined as the maximum on-study value. High = Higher than the upper limit of the normal range, Low = Lower than the lower limit of the normal range, Normal = within the lower and upper limits of the normal range. Percentages are based on the number of subjects in each treatment/analysis group.

Source Data: Listing 2.7.1

Table 1.7.2.1
Renal Function Tests
Safety Population

Repeat of 1.7.1.1

Note: Baseline is defined as last available value prior to ther first dose of study medication for a particular treatment.

¹Change from baseline: post-baseline value - baseline value. For the change from baseline, only subjects with a value at both the baseline visit and the specific post-baseline visit are included. Source Data: Listing 2.7.2

<DIRECTORY PATH>PROGRAM NAME Executed: DDMMMYYYY hh:mm

Parameters: Blood Urea Nitrogen, Creatinine, Estimated GFR - MDRD, Estimated GFR - Cockcroft-Gault

Table 1.7.2.2

Renal Function Tests - Shifts from Baseline to Worst On-Study Value
Safety Population

Repeat of 1.7.1.2

Source Data: Listing 2.7.2

Note: Baseline is defined as last available value prior to ther first dose of study medication for a particular treatment. The worst value is defined as the minimum on-study value. High = Higher than the upper limit of the normal range, Low = Lower than the lower limit of the normal range, Normal = within the lower and upper limits of the normal range. Percentages are based on the number of subjects in each treatment/analysis group.

Table 1.8
Vital Signs
Safety Population

Parameter: XXXXX (units)

·	·	340mg	≥340mg	
	Placebo	Placebo ADS-5102		ADS-5102
	(N=xx)	(N=xx)	(N=xx)	(N=XX)
Baseline				
n	XX	xx	xx	XX
Mean	XX.X	XX.X	xx.x	XX.X
SD	XX.XX	xx.xx	xx.xx	XX.XX
Median	XX.X	xx.x	xx.x	XX.X
Min, Max	XX, XX	XX, XX	XX, XX	XX, XX
linimum				
n	XX	xx	xx	XX
Mean	XX.X	XX.X	XX.X	XX.X
SD	XX.XX	XX.XX	XX.XX	XX.XX
Median	XX.X	XX.X	XX.X	XX.X
Min, Max	XX, XX	XX, XX	XX, XX	xx, xx
Maximum				
n	XX	xx	xx	XX
Mean	XX.X	XX.X	XX.X	XX.X
SD	xx.xx	xx.xx	xx.xx	XX.XX
Median	XX.X	XX.X	XX.X	XX.X
Min, Max	xx, xx	xx, xx	xx, xx	XX, XX

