Adverse Events Leading to Study Drug Discontinuation
Safety Population

Same layout as X.X

¹Duration (Days = Stop date - Start date + 1). Adverse events are coded using MedDRA Version 17.0.

<DIRECTORY PATH>PROGRAM NAME Executed: DDMMMYYYY hh:mm

Listing 2.7.1
Laboratory Results - Liver Function Tests
Safety Population

Subject Identifier	Study Identifier	Treatment	Sample Date	Laboratory Test	Result	Units	Flag	Normal Range
XXXXX-XX-X-XXX	XXXXX	260mg ADS-5102	DDMMMYYYY	XXXXXXXXXXXXXXX	XXX.X	XXXXX		XXX.X-XXX.X
				XXXXXXXXXXXXXX	XXX.X	XXXXX		XXX.X-XXX.X
			DDMMMYYYY	XXXXXXXXXXXXXX	XXX.X	XXXXX	L*	XXX.X-XXX.X
				XXXXXXXXXXXXX	XXX.X	XXXXX		XXX.X-XXX.X
	XXXXX	340mg ADS-5102	DDMMMYYYY	xxxxxxxxxxxx	XXX.X	XXXXX	Н	XXX.X-XXX.X
				XXXXXXXXXXXXXX	XXX.X	XXXXX	Н	XXX.X-XXX.X
			DDMMMYYYY	XXXXXXXXXXXXXX	XXX.X	XXXXX		XXX.X-XXX.X
				XXXXXXXXXXXXXX	XXX.X	XXXXX		XXX.X-XXX.X

Note: H = Above Normal Range, L = Below Normal Range, N = Normal, * indicates minimum value

<DIRECTORY PATH>PROGRAM NAME Executed: DDMMMYYYY hh:mm

Listing 2.7.2

Laboratory Results - Renal Function Tests
Safety Population

Same as X.X

Listing 2.8
Vital Sign Results
Safety Population

Subject Identifier				Blood Pressure(mmHg)				
	Study Identifier	Treatment	Test Date	Sitting Systolic/Diastolic	Standing Systolic/Diastolic	Heart Rate (bpm)	Height (cm)	Weight (kg)
XXXXX-XX-X-XXX	XXXXX	260mg ADS-5102	DDMMMYYYY DDMMMYYYY	xx/xx xx/xx	xx/xx	xxx xxx	XXX.X	XX.X
		340mg ADS-5102	DDMMMYYYY	xx/xx	xx/xx	XXX	XXX.X	XX.X

[figure not shown]
Heart Rate (bpm=beats/minute)

ADS-5102 Integrated Summary of Safety

- Figure 3.1 Kaplan-Meier Analysis of Time to Study Drug Discontinuation Safety Population
- Figure 3.6.1.1 Kaplan-Meier Analysis of Time to Onset of AE (Neuropsychiatric) Safety Population
- Figure 3.6.1.2 Kaplan-Meier Analysis of Time to Onset of AE (Neuropsychiatric) by Gender Safety Population
- Figure 3.6.1.3 Kaplan-Meier Analysis of Time to Onset of AE (Neuropsychiatric) by Age Safety Population
- Figure 3.6.1.4 Kaplan-Meier Analysis of Time to Onset of AE (Neuropsychiatric) by Race Safety Population
- Figure 3.6.1.5 Kaplan-Meier Analysis of Time to Onset of AE (Neuropsychiatric) by Baseline Renal Function Safety Population
- Figure 3.6.1.6 Kaplan-Meier Analysis of Time to Onset of AE (Neuropsychiatric) by Weight Safety Population
- Figure 3.6.1.7 Kaplan-Meier Analysis of Time to Onset of AE (Neuropsychiatric) by Baseline MAO-B Inhibitor Medications Safety Population

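### No planned integrated liver table counts subjects above a multiple of ULN, or with transaminase and bilirubin both raised

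*SAP*

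**What the plan says.** SAP 9.3 integrates only liver and renal laboratory parameters and leaves the rest to the study reports. On categories it states: "All clinical laboratory measures will be classified as Low, Normal, or High, or Normal/Abnormal according to the normal ranges". On the continuous summary it states: "Maximum on-treatment values will be summarized for the liver function parameters", and "For both groups, the change from baseline to the maximum/minimum value will be presented". SAP Section 9 adds "No formal statistical testing is planned", so the descriptive outputs are the whole analysis.

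The shells implement this as follows.

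- **Table 1.7.1.1** has one page per parameter. It gives n, mean, SD, median, minimum and maximum of the baseline value, of the maximum and of the change, in raw units.
- **Table 1.7.1.2** is a shift table with Low, Normal, High and Missing, again per parameter. Its note reads: "The worst value is defined as the maximum on-study value. High = Higher than the upper limit of the normal range".
- **Listing 2.7.1**, the named source of both tables, prints each result with sample date, units, flag and normal range. Its footnote reads: "Note: H = Above Normal Range, L = Below Normal Range, N = Normal, * indicates minimum value".

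The SAP's lists of tables and figures contain no other liver summary.

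The one ULN multiple in the documents is an entry limit. Protocol 7.2.2 and 7.2.3 exclude subjects with "Aspartate aminotransferase (AST) and/or alanine aminotransferase (ALT) > 2 times the upper limit of normal". Under Protocol 12.3, out-of-range laboratory findings "per se are not reported as AEs". They become AEs when judged clinically significant or accompanied by signs or symptoms.

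**The concern.** This SAP is the integrated safety summary for a submission. A reader of its liver section will want to know, for each treatment column, how many subjects had a marked transaminase rise and how many had transaminase and bilirubin raised together. A single High category answers neither question. Because Groups 2 and 3 can enter already above ULN, it can also show a large rise as no shift and a negligible one as a shift. Without a specified table, such counts would have to be made afterwards, with cut-offs chosen once the data are known.

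**Working it through.** The documents give no figure to reproduce here, so the check is whether the planned tables determine the missing counts.

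**1. What the shift table prints.** Protocol Table 6 schedules serum chemistry at Screening and not at Week 0. For Groups 2 and 3 the PD302 baseline under SAP 7.6 is therefore the screening value, which may be as high as 2 x ULN for ALT/AST.

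| Baseline (x ULN) | Maximum (x ULN) | Cell in Table 1.7.1.2 |
|---|---|---|
| 1.9 | 10 | High to High |
| 0.95 | 1.05 | Normal to High |

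**2. Do Tables 1.7.1.1 and 1.7.1.2 together fix a count above a threshold?** Assumptions, not from the documents: 100 subjects, common ULN 40 U/L, every baseline 25 U/L. In both sets, 45 subjects have a maximum of 25, 45 have 30 and one has 200. The other nine differ:

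- Set A: 110, 126 and 130, three subjects each
- Set B: 114, 118 and 134, three subjects each

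The nine sum to 3 x (110 + 126 + 130) = 1,098 in A and 3 x (114 + 118 + 134) = 1,098 in B. Their sums of squares also agree: 3 x 44,876 = 134,628 in both.

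| Entry | Set A | Set B |
|---|---|---|
| Maximum: mean (SD) | 37.73 (31.92) | 37.73 (31.92) |
| Maximum: median; range | 30; 25 to 200 | 30; 25 to 200 |
| Change: mean (SD) | 12.73 (31.92) | 12.73 (31.92) |
| Change: median; range | 5; 0 to 175 | 5; 0 to 175 |
| Normal to High | 10 | 10 |
| **Subjects above 3 x ULN (120 U/L)** | **7** | **4** |

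The same construction at the protocol's 2 x ULN (80 U/L) uses 70, 86 and 90 against 74, 78 and 94. Both sets then have mean 34.13, SD 23.21, median 30, maximum 200 and 10 shifts, with 7 against 4 subjects above 80. The 3 x ULN cut-off is illustrative only.

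**3. Joint elevation.** Suppose 5 of 100 exceed a transaminase limit and 5 of 100 a bilirubin limit. The number exceeding both lies between max(0, 5 + 5 - 100) = 0 and min(5, 5) = 5. Separate tables are compatible with every value in that range.

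**4. Illustration of noise in the High category.** Assume ULN is the 97.5th percentile, values are log-normal with CV 40%, and there is no drug effect. With k independent samples, P(at least one High) = 1 - 0.975^k. Protocol Table 6 schedules 10 post-baseline samples. The 5 placebo-period samples are an assumption. The correlated cases were simulated with 400,000 subjects.

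| Samples | Correlation 0 | 0.5 | 0.8 |
|---|---|---|---|
| 5 | 11.9% | 9.2% | 6.4% |
| 10 | 22.4% | 14.4% | 8.6% |

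P(maximum above 2 x ULN) was at most 0.09% in every case. Under these assumptions the High percentage rises with length of follow-up alone, and a count above 2 x ULN hardly does.

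**The case against.** The strongest reply is that nothing is hidden. Four parts of it stand.

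- **Listing 2.7.1** carries every result with its own normal range, so ULN multiples and joint rises can be worked out by hand. A reader might infer that the outputs as a whole cannot show marked rises. They can. What is missing is a specified summary.
- **Table 1.7.1.1** prints the largest on-treatment value and the largest change. The 1.9 to 10 x ULN subject would show there unless a larger change exists. If the column maximum lies below a cut-off at the lowest applicable ULN, the count is zero and a bound follows: 0 of 250 gives 1 - 0.05^(1/250) = 1.2% (one-sided 95%). It would therefore be wrong to infer that no planned table supports a zero-count statement. Moreover, 250 is PD302's enrolment ceiling and not the integrated N. A non-zero count remains undetermined, as step 2 shows.
- **AE tables** do capture some rises, because Protocol 12.3 requires clinically significant or symptomatic findings to be recorded and accepts that a finding without symptoms can qualify. This route depends on investigator judgement and gives no count at a fixed threshold.
- **No hepatic signal is reported.** Protocol 4.4 describes no notable pattern in serum chemistry, and the SAP's events of special interest are neuropsychiatric, falls and hallucinations. This limits the priority. Even so, SAP 9.3 itself selects liver parameters for integration.

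Two further inferences should be resisted. Group 1 has no ALT/AST limit in Protocol 7.2.1, but these subjects come from an efficacy study whose entry criteria are not in these documents, so nothing here rests on Group 1. The minimum-value asterisk does not corrupt any count either: SAP 9.3 and the Table 1.7.1.2 note both specify the maximum for liver tests.

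**Conclusion.** The point holds for the planned tables. None gives n (%) above any ULN multiple or with joint transaminase and bilirubin elevation, and the two liver tables together do not determine those counts (7 against 4 per 100 from identical entries; 0 to 5 for the joint count). The constructed sets rest on the stated N, ULN and baselines, and they prove non-identifiability without predicting any result.

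A reader might go further and take the High counts to be mostly chance excursions. The documents do not support that as a fact. It depends on an assumed CV, ULN percentile, absence of drug effect and number of samples. The analysis runs at a PD302 database freeze (SAP Section 4) whose date is not given. From the study start of 14 July 2014 to the SAP date of 13 November 2015 is 487 days, about 70 weeks. At that date a PD302 subject could have had at most 7 scheduled post-baseline samples in PD302 (through Week 64), for which independence gives 1 - 0.975^7 = 16%.

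This is a worthwhile, inexpensive improvement to the integrated summary. It does not invalidate what is planned.

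**What to change.** 1. In Table 1.7.1.2, split High for ALT, AST and bilirubin into pre-specified multiples of each sample's own ULN, at baseline and at the on-treatment maximum. Include 2 x ULN, the protocol's entry limit. The higher cut-offs have no source in the documents and are for the sponsor to pre-specify.
2. Add one cross-tabulation, one entry per subject, of maximum ALT or AST (x ULN) against maximum bilirubin (x ULN), by treatment/analysis group.
3. As a minor shell correction, make the asterisk in Listing 2.7.1 mark the maximum.

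Results and normal ranges are already in Listing 2.7.1, so no new data are needed. The cost is shell wording, one extra table, and a longer shift table in which several rows will be sparse.

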### **8.8.** Concomitant Medications

Information regarding medications taken by the subject within 30 days prior to the Screening Visit and throughout the study will be collected and recorded on the Prior/Concomitant Medications CRF. This information will include the name of the medication, dosage information (including frequency and route of administration), dates taken, reason for use, and stop date, if available.

All subjects must be on a stable regimen of antiparkinson's medications for at least 30 days prior to screening, including any levodopa preparation dosed at least three times daily.

Any other current and allowed prescription/non-prescription medications and/or nutritional supplements must have been at a stable dose and frequency for at least 30 days prior to

Page 37 of 74

screening. (This criterion does not apply to medications that are taken on an as-needed basis only).

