7.1 Derived and Transformed Data

Details on derivations and transformations for each individual study are specified in the study SAPs. The study teams have worked closely to ensure consistent algorithms were implemented across studies. Modifications to study algorithms are not planned for data integration. In the rare instance where modifications to specific algorithms are necessary to facilitate programming, documentation will be provided in the data definition tables and reviewer's guide.

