7.5 Subgroup Definitions

The following subgroups will be explored for key safety analyses:

- Gender
- Age ($<65, \ge 65, \ge 65$ to $<75, \ge 75$)
- Race (white, non-white)
- Baseline renal function (estimated GRF \leq 60 or estimated GFR \geq 60)
- Weight (< or \ge median)
- Baseline MAO-B inhibitor medications (Yes, No)
- Baseline Dopamine Agonist medications (Yes, No)
- Baseline levodopa dose (< or ≥ median)
- Time since PD diagnosis in years (< or \ge median)
- Age at PD diagnosis (< or \ge median)
- Prior Deep Brain Stimulation (Yes, No)
- Geographic Region (European Union vs North American)

For subgroups categorizations based on median values, a value for each treatment/analysis group will be calculated and subjects will be categorized separately for each treatment/analysis group in which they are included.

7.6 Definitions of Baseline, Analysis Day 1, and Study Day 1

The baseline assessment will be the last available assessment prior to the first dose of study medication for a particular treatment. For subjects receiving multiple treatments, baseline assessments will be defined for each treatment assignment. For subjects receiving 340 mg ADS-5102 in more than one study, the following logic will be applied to assign the baseline value:

- For subjects continuing into ADS-AMT-PD302 with no gap in treatment prior to enrollment, the baseline assessment will be the last available assessment prior to the first dose of 340 mg ADS-5102 in any study.
- For subjects continuing in ADS-AMT-PD302 with a gap in treatment prior to enrollment, the baseline assessment will be the last available assessment prior to the first dose of 340 mg ADS-5102 in ADS-AMT-PD302. Assessments from the first study in which the subject enrolled will not be considered for assignment as baseline.

An overall baseline value will be determined and used in summaries were overall values are calculated and displayed. This value will be assigned following the same logic outlined previously, but study treatment will not be considered in the selection of this value.

Analysis Day 1 is defined as the date of the baseline visit. Subjects should be dispensed the study drug at the baseline visit and presumably take the first dose at bedtime on the same day. No Day 0 is defined. Negative study days indicate observations were obtained prior to treatment.

Study Day 1 is defined as the date of the first dose of study drug for the individual study in which the subject participated.

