8.4 Medical History

General medical history data will not be integrated. Summaries are provided in the individual study results.

Parkinson's disease history data including the following will be integrated, listed, and summarized for the Safety population by treatment/analysis group and overall.

- Age (years) at PD diagnosis
- Time since PD diagnosis in years
- Age (years) at start of levodopa treatment
- Duration of levodopa treatment in years
- Duration of levodopa-induced dyskinesia in years
- Baseline Levodopa dose

For the duration of Parkinson's disease, if only the month and year of diagnosis is available, the 15th day of the indicated month is assumed, and when only the year of diagnosis is available, July 1 of the indicated year is assumed. A similar algorithm is used for age at PD diagnosis, age at start of levodopa treatment, duration of levodopa treatment, and duration of levodopa—induced dyskinesia. Fractional years of duration will be used for the analyses.

8.5 **Prior and Concomitant Medications**

Prior medications are defined as medications with a stop date occurring before the first dose date. Concomitant medications are defined as medications with a stop date occurring on or after the first dose date, or listed as ongoing. Medications with start and stop dates (or ongoing) which bracket the first dose date will be summarized as both prior and concomitant medications.

All non-study drugs (including prescribed and over the counter medications) taken are collected on the CRFs for the individual studies.

Prior and concomitant medication data will be integrated, listed, and summarized by Anatomical Therapeutic Chemical (ATC) Level and preferred term (PT) by treatment/analysis group for the Safety population. At each level of summarization, a subject is counted once if he/she reported one or more medications at that level. The PD prior and concomitant medications will be presented separately.

For the purpose of classifying medications as prior and/or concomitant in summaries, incomplete medication start and stop dates will be imputed as detailed below:

- If year and month are present and day is missing then set start day to last day of month, and set end day to the later of (first day of month, start day)
- If year and day are present and month is missing then set start month to December, and set end month to the later of (January, start month)

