ge at start of levodopa treatment (yrs)					
n	XX	XX	XX	XX	XX
Mean	XX.X	XX.X	XX.X	XX.X	XX.X
SD	XX.XX	XX.XX	XX.XX	XX.XX	XX.XX
Median	XX.X	XX.X	XX.X	XX.X	XX.X
Min, Max	XX, XX				

Note: Durations calculated using diagnosis/start/onset dates.

Source Data: Listing 2.3.1

<DIRECTORY PATH>PROGRAM NAME Executed: DDMMMYYYY hh:mm

Table 1.3.1
Parkinson's Disease History
Safety Population

		340mg ADS-5102 (N=xx)	≥340mg ADS-5102 (N=xx)	ADS-5102 (N=xx)	All (N=xx)
	Placebo (N=xx)				
Duration of levodopa treatment (yrs)					
N	XX	XX	XX	XX	XX
Mean	XX.X	XX.X	XX.X	XX.X	XX.X
SD	XX.XX	XX.XX	XX.XX	XX.XX	xx.xx
Median	XX.X	XX.X	XX.X	XX.X	XX.X
Min, Max	XX, XX	xx, xx	XX, XX	xx, xx	XX, XX
Duration of levodopa-induced dyskinesia					
N	XX	XX	XX	XX	XX
Mean	XX.X	XX.X	XX.X	XX.X	XX.X
SD	XX.XX	XX.XX	XX.XX	XX.XX	XX.XX
Median	XX.X	XX.X	XX.X	XX.X	XX.X
Min, Max	XX, XX	XX, XX	xx, xx	xx, xx	XX, XX
Baseline levodopa (any preparation) dose (mg)					
n	XX	XX	XX	XX	XX
Mean	XX.X	XX.X	XX.X	XX.X	XX.X
SD	XX.XX	XX.XX	XX.XX	XX.XX	XX.XX
Median	XX.X	XX.X	XX.X	XX.X	XX.X
Min, Max	XX, XX	XX, XX	xx, xx	xx, xx	XX, XX
< median n (%)	xx (xx.x)	xx (xx.x)	xx (xx.x)	xx (xx.x)	xx (xx.x)
≥ median n (%)	xx (xx.x)	xx (xx.x)	xx (xx.x)	xx (xx.x)	xx (xx.x)

Note: Durations calculated using diagnosis/start/onset dates.

Source Data: Listing 2.3.1

Table 1.3.2
Parkinson's Disease Related Baseline Characteristics
Safety Population

	340mg ≥340mg						
	Placebo (N=xx)	ADS-5102 (N=xx)	ADS-5102 (N=xx)	ADS-5102 (N=xx)	All (N=xx)		
MDS-UPDRS: Part I							
n	XX	XX	XX	XX	XX		
Mean	XX.X	XX.X	XX.X	XX.X	xx.x		
SD	XX.XX	XX.XX	XX.XX	XX.XX	XX.XX		
Median	XX.X	XX.X	XX.X	XX.X	xx.x		
Min, Max	xx, xx	xx, xx	xx, xx	xx, xx	XX, XX		
MDS-UPDRS: Part II							
n	XX	XX	XX	XX	XX		
Mean	XX.X	XX.X	XX.X	XX.X	XX.X		
SD	XX.XX	XX.XX	XX.XX	XX.XX	XX.XX		
Median	XX.X	XX.X	XX.X	XX.X	XX.X		
Min, Max	xx, xx	xx, xx	XX, XX	XX, XX	XX, XX		
MDS-UPDRS: Part III							
n	XX	XX	XX	XX	XX		
Mean	XX.X	XX.X	XX.X	XX.X	XX.X		
SD	XX.XX	XX.XX	XX.XX	XX.XX	XX.XX		
Median	XX.X	XX.X	XX.X	XX.X	XX.X		
Min, Max	XX, XX	XX, XX	xx, xx	xx, xx	XX, XX		
MDS-UPDRS: Combined (Part I, II, and III)							
n	XX	XX	XX	XX	XX		
Mean	XX.X	XX.X	XX.X	XX.X	XX.X		
SD	XX.XX	XX.XX	XX.XX	XX.XX	XX.XX		
Median	XX.X	XX.X	XX.X	XX.X	XX.X		
Min, Max	XX, XX	XX, XX	XX, XX	XX, XX	XX, X		

Source Data: Listings 2.3.2, 2.3.3

Table 1.3.2
Parkinson's Disease Related Baseline Characteristics
Safety Population

		340mg	≥340mg	ADS-5102 (N=xx)	All (N=xx)
	Placebo (N=xx)	ADS-5102 (N=xx)	ADS-5102 (N=xx)		

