Subject Identifier	Study Identifier	Treatment	Age at PD Diagnosis (yrs.)	Time Since PD Diagnosis (yrs.) ¹	Age at Start of Levodopa Treatment (yrs.)	Duration of Levodopa Treatment (yrs.) ¹	Duration of LID (yrs.) ¹	Baseline Levodopa Dose (mg) ²
XXXXX-XX-X-XXX	XXXXX	Placebo	XX	X	X	X • X	X . X	XX.X
	XXXXX	340mg ADS-5102	XX	X	X	X . X	X . X	XX.X
XXXX-XX-XXX	XXXXX	260mg ADS-5102	XX	X	X	X . X	X . X	XX.X
XXXXX-XX-XXX	XXXXX	420mg ADS-5102	XX	X	X	X . X	X . X	XX.X

Note: PD = Parkinson's disease, LID = Levodopa-induced dyskinesia, # indicates an imputed date.

¹Time since Parkinson's disease diagnosis = (Analysis Day 1 - Date of diagnosis of Parkinson's disease)/ 365.25. When only the month and year of diagnosis are available, the 15th day of the indicated month is assumed, and when only the year of diagnosis is available, July 1 of the indicated year is assumed. A similar algorithm is used for duration of levodopa treatment, and duration of levodopa-induced dyskinesia.

 2 Baseline total levodopa dosage is defined as the levodopa medication (any preparation) with last start date prior to first dose of study medication.

Listing 2.3.2
Parkinson's Disease-Related Baseline Characteristics (Part I)
Safety Population

Subject Identifier	Study Identifier	Treatment	MDS-UPDRS Part I	MDS-UPDRS Part II	MDS-UPDRS Part III	MDS-UPDRS Combined	MDS-UPDRS Part IV
XXXXX-XX-X-XXX	XXXXX	Placebo	XX	Х	Х	X . X	X . X
	XXXXX	340mg ADS-5102	XX	X	X	X.X	X • X
XXXXX-XX-XXX	XXXXX	260mg ADS-5102	XX	X	X	X.X	X • X
XXXXX-XX-XXX	XXXXX	420mg ADS-5102	XX	X	Х	X.X	X.X

Note: PD = Parkinson's disease, LID = Levodopa-induced dyskinesia, # indicates an imputed date.

¹Time since Parkinson's disease diagnosis = (Analysis Day 1 - Date of diagnosis of Parkinson's disease)/ 365.25. When only the month and year of diagnosis are available, the 15th day of the indicated month is assumed, and when only the year of diagnosis is available, July 1 of the indicated year is assumed. A similar algorithm is used for duration of levodopa treatment, and duration of levodopa-induced dyskinesia.

 2 Baseline total levodopa dosage is defined as the levodopa medication (any preparation) with last start date prior to first dose of study medication.

Listing 2.3.3
Parkinson's Disease-Related Baseline Characteristics (Part II)
Safety Population

Subject	Study		MDS-UPDRS Part IV	MDS-UPDRS Part IV	MMSE	Hoehn and
Identifier	Identifier	Treatment	Item 4.1	Item 4.2	Score	Yahr Stage
XXXXX-XX-X-XXX	XXXXX	Placebo	XX	Х	Х	X • X

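### The SAP's baseline *total* levodopa dose is taken from a single medication record, so subjects on concurrent levodopa preparations are under-recorded and the levodopa safety subgroups are split on a faulty value

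*SAP*

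**What the plan says.** The variable appears in four places in the SAP.

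- **Section 7.5** makes it a subgroup factor for key safety analyses: "Baseline levodopa dose (< or ≥ median"). For factors cut at a median, the section adds that "a value for each treatment/analysis group will be calculated and subjects will be categorized separately for each treatment/analysis group in which they are included".
- **Section 8.4** lists it by name only ("Baseline Levodopa dose"), with no derivation.
- **Table 1.3.1** has a row labelled "Baseline levodopa (any preparation) dose (mg"), with n, mean, SD, median, range and counts on each side of the median.
- **Listing 2.3.1, footnote 2** gives the rule: "Baseline total levodopa dosage is defined as the levodopa medication (any preparation) with last start date prior to first dose of study medication". The footnote is repeated under Listing 2.3.2, which has no levodopa column.

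SAP 7.1 adds that "Details on derivations and transformations for each individual study are specified in the study SAPs". Those study SAPs are not among the documents.

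On the data side, Protocol 8.8 requires a stable antiparkinson regimen, "including any levodopa preparation dosed at least three times daily". Nothing in the entry criteria limits a subject to one levodopa product. For each medication the case report form records the name, "dosage information (including frequency and route of administration), dates taken, reason for use, and stop date, if available".

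**The concern.** The label and the rule disagree. A total across preparations needs a sum, but the footnote picks the one levodopa entry that started last. The words in brackets about preparations widen which products qualify; they do not say that doses are added. A subject on a daytime product plus a bedtime product started later is therefore assigned the bedtime dose alone.

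The rule has three further gaps:

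- Two records with the same latest start date give no unique dose.
- A record that stopped before first dose is not excluded.
- Neither the footnote nor Table 1.3.1 says whether the figure is per administration or per day.

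At stake are the dose row of Table 1.3.1 and every output split by this factor: Tables 1.6.1.9 and 1.6.2.9 (adverse events overall, and by system organ class and preferred term), Tables 1.6.10.10, 1.6.11.10 and 1.6.12.10 (time to neuropsychiatric events, falls and hallucinations), and Figures 13.6.1.9, 3.6.2.9 and 3.6.3.9. If levodopa load is related to those events, a split that puts high-dose subjects in the low-dose half will tend to hide it.

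**Working it through.** The plan states no figure on this point, so there is none to reproduce. The check applies the rule literally and then asks how far the error could spread.

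**1. One subject.** Let the concurrent daily doses be d₁, …, dₖ, with dₖ started last. The true total is Σdᵢ and the footnote gives dₖ. The shortfall is the sum of the other doses, which is always above zero. Invented example: 100 mg three times daily plus 200 mg at bedtime started later. True total = 3 × 100 + 200 = 500 mg; recorded = 200 mg, or 40%.

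**2. The cut moves too.** Invented six-subject group: five subjects on one preparation at 400, 600, 700, 800 and 900 mg, and subject E on 750 mg plus a later-started 200 mg.

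| Rule | Value for E | Sorted doses (mg) | Median | Upper half |
|---|---|---|---|---|
| Sum | 950 | 400, 600, 700, 800, 900, 950 | (700 + 800)/2 = 750 | 800, 900, E |
| Footnote | 200 | 200, 400, 600, 700, 800, 900 | (600 + 700)/2 = 650 | 700, 800, 900 |

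E falls to the lower half, and the 700 mg subject, whose dose is recorded correctly, rises to the upper half. One under-recorded subject misplaces two of six.

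**3. A whole group, under assumptions.** None of these inputs is in the documents:

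- q, the share of subjects on more than one preparation: 10%, 20% or 40%.
- f, the share of the true total held by the last-started record: uniform from 20% to 60%, mean 0.40.
- True total: lognormal, median 700 mg, log-SD 0.5, independent of q and f.

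Mean dose: recorded/true = 1 − q(1 − 0.40) = 1 − 0.6q.

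Misplaced share: only multi-preparation subjects can move down, and half of them are truly in the upper half. Let h be the proportion of that half that drops. Equal numbers move up to refill the upper half, so the misplaced share is m = 2 × q × ½ × h = q × h. Simulation supplies h and m.

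| q | Recorded/true mean | h | q × h | Simulated m |
|---|---|---|---|---|
| 10% | 0.94 | 88% | 8.8% | 8.8% |
| 20% | 0.88 | 84% | 16.8% | 16.9% |
| 40% | 0.76 | 72% | 28.8% | 28.9% |

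Since h cannot exceed 1, m cannot exceed q under these assumptions. If only 2% to 5% take more than one preparation, at most 2% to 5% of subjects change half.

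**4. Other inputs.** With the last-started record holding a fixed 20% or 50% of the total and a coefficient of variation of 0.4 to 0.6, the misplaced share is about 8–10%, 14–20% and 23–48% for q = 10%, 20% and 50%.

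**5. Effect on a subgroup contrast.** Suppose event risk depends only on the true half: 20% in the low half and 30% in the high half. A share 1 − m of each recorded half is placed correctly, so the observed difference is 10 × (1 − 2m) points: 10 × (1 − 0.176) = 8.2, 10 × (1 − 0.338) = 6.6 and 10 × (1 − 0.578) = 4.2 points at q = 10%, 20% and 40%. The contrast shrinks but keeps its sign.

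**The case against.** **The wording may be shorthand.** Equating a dosage with a medication is loose, and the author may have meant the total regimen as of the last change before first dose. The study SAPs cited in SAP 7.1 may already sum concurrent records. This stands as a reason not to claim that the programmed value will be wrong. It does not rescue the text: the footnote is the only rule in these documents, and nothing in SAP 7.1 overrides it. Taking the last start date suits a dose change in one product; with two products it drops the other.

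**The size is assumed.** This stands in full. The documents give no share on multiple preparations, and the effect could be small.

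**The stopped-record case is unlikely in ADS-AMT-PD302.** This largely stands. Protocol 8.8 asks for 30 days of stable antiparkinson treatment before screening and collects medications from that same window. A reader might also infer that every error is downward. That holds for concurrent ongoing records; a stopped record could push the value either way.

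**A reader might infer that the subgroup pattern would be reversed.** The documents hold nothing to support that. In the check above, adding an extra 10-point risk for multi-preparation use itself changed the sign only at q = 40%. The documents give no source for such an excess.

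**The stakes are limited.** SAP 9 plans no formal testing, and this is one of 12 exploratory factors. The main adverse event and exposure tables do not use it, and Listing 2.4 still shows the individual medication records.

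**Conclusion.** The point holds. As written, the rule gives a value below the true total for every subject with concurrent levodopa preparations started on different dates, and that follows from the text alone. Through the median cut it also misplaces some single-preparation subjects, which tends to weaken any relation between levodopa dose and adverse events.

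How many subjects are affected cannot be taken from the documents. The figures of about 9%, 17% and 29% changing half are illustrations that depend on the assumed 10%, 20% and 40% and on the assumed dose distribution. The consequence is confined to one baseline row and one set of descriptive subgroup outputs. No main safety conclusion rests on it, and neither reversal of a subgroup pattern nor a uniformly downward error is shown.

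**What to change.** Replace the footnote under Listing 2.3.1, delete its repeat under Listing 2.3.2, and put the rule in SAP 7.5 or 8.4:

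> Baseline total daily levodopa dose (mg/day) = sum, over all levodopa records that started before and were ongoing at the first dose used to define baseline for that treatment/analysis group under SAP 7.6, of levodopa content per administration × administrations per day.

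Use this value in Table 1.3.1, Listing 2.3.1 and the median split, and relabel the table row in mg/day. The link to SAP 7.6 is needed because baseline there is set per treatment, and differently for rollover subjects with and without a treatment gap. Summing also removes the problem of tied start dates. The same paragraph should say how as-needed levodopa, missing frequencies and partial dates are handled, since SAP 8.5 imputes dates only to classify medications as prior or concomitant.

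The cost is one derivation in the analysis dataset, with those conventions written down. Dose, frequency and dates are already collected under Protocol 8.8 and shown in Listing 2.4, so no new data are needed. If the study-level programs already sum concurrent records, only the text changes.
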